**LIST OF ABBREVIATIONS AND RELEVANT DEFINITIONS**

ABR	ABR form, General Assessment and Registration form, is the application form required for submission to the accredited Ethics Committee In Dutch, ABR = Algemene Beoordeling en Registratie
AE	Adverse Event Any untoward medical occurrence, unintended disease or injury, or untoward clinical signs (including abnormal laboratory findings) in subjects, users or other persons, whether or not related to the investigational medical device
AR	Adverse Reaction
CA	Competent Authority
Clinical Investigation	Systematic investigation in one or more subjects, undertaken to assess the safety and performance of a medical device
CIP	Clinical Investigation Plan Document that state(s) the rationale, objectives, design and proposed analysis, methodology, monitoring, conduct and record-keeping of the clinical investigation NOTE: The term "protocol" is synonymous with "CIP". However, protocol has many different meanings, some not related to clinical investigation, and these can differ from country to country.
CFA	Confirmatory factor analyses
CFR	Code of Federal Regulations
CNS	Central Nervous System
COWAT	Controlled Oral Word Association Test
CRF	Case Report Form Set of printed, optical or electronic documents for each subject on which information to be reported to the sponsor is recorded, as required by the CIP
CV	Curriculum Vitae
DCDx	Digital Cognitive Diagnostics
DSMB	Data Safety Monitoring Board
EC	Ethics Committee
eCRF	Electronic Case Report Forms
ECT	Electroconvulsive therapy,
EDC	Electronic Database Capture
Endpoint	Principal indicator(s) used for assessing the primary hypothesis of a clinical investigation
EU	European Union
FDA	Food and Drug Administration
GCP	Good Clinical Practice
HCP	HealthCare Professional
HSDP	HealthSuite Digital Platform (Philips)
Hypothesis	Testable statement, resulting from the objective, regarding the investigational medical device safety or performance used to design the clinical investigation and that can be accepted or rejected based on results of the clinical investigation and statistical calculations. NOTE: The primary hypothesis is the determinant of the investigational medical device safety or performance parameters and is usually used to calculate the sample size. Secondary hypotheses concerning other points of interest can also be evaluated.
ADL	Activity of Daily Living
IB	Investigator's Brochure
IC	Informed Consent The informed consent is documented by means of a written, signed and dated informed consent form. The informed consent process is the process by which an individual is provided information and is asked to voluntarily participate in a clinical investigation.
ID	Identification
IRB	Institutional Review Board
ISC	IntelliSpace Cognition

Title: Clinical Investigation Plan		Author: [name]		Company Restricted	
DocID: ICBE-2-28674	Version: 2.0	Date: 2019-02-18	Status: Approved	Page: 5 of 35	
IRBMANAGER PILOT – QI PROJECT					

Investigator	Individual member of the investigation site team designated and supervised by the principal investigator at an investigation site to perform critical clinical-investigation-related procedures or to make important clinical investigation- related decisions. NOTE: An individual member of the investigation site team can also be called "sub-investigator" or "co-investigator".
MMSE-2	Mini Mental Status Exam 2
MoCA	The Montreal Cognitive Assessment
Objective	Main purpose for conducting the clinical investigation
Point of enrollment	Time at which, following recruitment, a subject signs and dates the informed consent form
QMS	Quality Management System
ROCFT	Rey Osterrieth Complex Figure Test
SAE	Serious Adverse Event Adverse event that a) led to death, b) led to serious deterioration in the health of the subject, that either resulted in 1) a life-threatening illness or injury, or 2) a permanent impairment of a body structure or a body function, or 3) in-patient or prolonged hospitalization, or 4) medical or surgical intervention to prevent life-threatening illness or injury or permanent impairment to a body structure or a body function, c) led to foetal distress, foetal death or a congenital abnormality or birth defect NOTE Planned hospitalization for a pre-existing condition, or a procedure required by the CIP, without serious deterioration in health, is not considered a serious adverse event.
Sponsor	Individual or organization taking responsibility and liability for the initiation or implementation of a clinical investigation
TBI	Traumatic Brain Injury
TMT	Trail Making Test
USA	United States of America

Title: Clinical Investigation Plan		Author: [name]		Company Restricted	
DocID: ICBE-2-28674	Version: 2.0	Date: 2019-02-18	Status: Approved	Page: 6 of 35	
IRBMANAGER PILOT – QI PROJECT					

## 1 1 EXECUTIVE SUMMARY

Study Title & ID	PJ-011726 Psychometric properties of IntelliSpace Cognition  Full title: Study to establish the psychometric properties of the digital cognitive tests on the Philips IntelliSpace Cognition Platform
Project Name	N/A
Brief Summary of Study Provide a lay-language abstract of your study plan (100-300 words)	This study aims to validate the tests that are on the IntelliSpace Cognition platform and to establish normative data for these tests.
Key Words Associated with Study Provide 3-5 PubMed MeSH keywords	Cognitive model Cognitive assessment Digital cognitive tests Automated scoring Algorithms
Country(s) from where the data originates (where collected)	 Netherlands  USA  Germany  China  India  Belgium  UK  Kenya  Other:
ISO 14155 compliance	 This study will be conducted per the requirements of ISO 14155  This study WILL NOT be conducted per the requirements of ISO 14155. For example studies formerly known as H-lite and J-Lite  This study has no clinical primary or secondary objectives. However the data generated from this study will be used as ground data in a Device class II according to regulation CFR21 Sec. 882.1470 Computerized cognitive assessment aid.  Therefore Philips will follow ISO 14155, Good Clinical Practice in all applicable requirements.  Data generated from this trial will be monitored and will be Part 11 compliant.  Important note 1: There are no foreseeable risks or possible adverse events in this study. This is a non-significant risk study .  The study will be submitted to ICBE and IRB review /approval.
Is this study part of a student project/thesis?	 No  Yes, Student Name:                      University:
Primary objective	The study has four aims.

	
1. To compare the psychometrics of digital and paper-pencil cognitive tests. Score distributions, test-retest reliability, and construct validity of the following tests will be compared: Trail Making Test (TMT), Rey Osterrieth Complex Figure Test (ROCFT), Digit Span Test, Controlled Oral Word Association Test (COWAT), Category Fluency Test, Rey Auditory Verbal Learning Test (RAVLT), Clock Drawing Test, Star Cancellation Test, O Cancellation Test, Mini Mental Status Exam 2 (MMSE-2).
 
2. To assess the degree of agreement between the algorithm and manual scores for the digital Rey Osterrieth Complex Figure Test and Clock Drawing Test.

	
3. To estimate regression-based norms and reliable change indices.
 
4. To estimate factor loadings for a structural equation model describing cognition in terms of distinct cognitive domains

Secondary objective(s)
	
The secondary objective of the study is to explore usability aspects of IntelliSpace Cognition.

Participating parties and their roles
	
Sponsor: Philips Electronics Nederland B.V.,
 
 
• Internal Ethics approval
 
• Providing Principal Investigator
 
• Study Design
 
• Monitoring
 
• Data storage
 
• Data integrity check
 
• Data analysis
 
• Report
 
 
Study co-ordinator:
 
 
• Selection of rooms for data collection
 
• Selection of psychometrists
 
• IRB approval
 
• Recruitment of participants
 
• Data collection
 

Subjects
	
The study will include at minimum <math>N=400</math> and up to <math>N=450</math> healthy participants who will be sufficiently distributed across gender, ages 55 to 80 for validation data and ages 50 to 80 for normative data, ethnicity, and education level to reflect the distribution of people that will typically be assessed with IntelliSpace Cognition.
 
As this study is in preparation of selling a reliable product, we aim to obtain norms based on a sample that adequately reflects the US population.
 
A variety of standard techniques will be used to recruit participants.

Title: Clinical Investigation Plan		Author: [name]		Company Restricted	
DocID: ICBE-2-28674	Version: 2.0	Date: 2019-02-18	Status: Approved	Page: 8 of 35	
IRBMANAGER PILOT – QI PROJECT					

	
Inclusion Criteria:
 
 
• Examinee’s primary language (language most often spoken) must be English.
 
• If examinee has vision impairment or hearing loss, must be corrected to normal.
 
• Must have normal fine and gross motor ability
 
• Must have use of fingers, hands, and arms to be able to use a pencil to write symbols.
 
• Must be able to understand subtest instructions and participate fully in testing.
 

	
Exclusion Criteria:
 
 
• Evidence of current cognitive impairment.
 
• Disruptive behavior or insufficient compliance with testing to ensure a valid assessment.
 
• Examinee must not be currently admitted to a hospital, assisted living, nursing home or a psychiatric facility.
 
• Examinee must not be diagnosed with a neurological disorder or disease (e.g., Parkinson’s, brain tumor, stroke, TBI, epilepsy [if # seizures ≤ 2 and not receiving ongoing treatment for seizures, and not currently seeking medical evaluation or attention related to seizures, examinee can be accepted], encephalitis, dementia, language disorder (expressive or mixed receptive/expressive excluded; articulation disorder is ok), learning disorder.
 
• Must not have been unconscious related to traumatic brain injury or “medical condition” > 20 minutes (however, e.g., heat stroke, medication induced are ok) or any head-injury resulting in an overnight hospital stay.
 
• Any history of a medical event requiring resuscitation in which examinee was non-responsive for > 15 minutes.
 
• Must not have current or recent functional change (ability to carry out usual duties at work, in school, IADLs [driving, shopping, managing money], etc.) due to cognitive change.
 
• Examinee must not be receiving chemotherapy treatment, or have received chemotherapy treatment in the past 2 months.
 
• Examinee must not have a history of ECT or radiation to the CNS.
 
• Examinee must not be (currently or in the past) diagnosed with a psychotic disorder, or currently diagnosed with a mood disorder (however, Major Depressive Disorder in remission or with no current episode, and Dysthymic and Adjustment Disorders, are acceptable) or an anxiety disorder with symptoms significant enough to interfere with optimal test performance.
 
• Autoimmune disorder (e.g., LUPUS, Multiple Sclerosis)
 
• Examinee must not be currently diagnosed with substance abuse or dependence, or have carried any substance abuse or dependence diagnosis in the past year (> 1 year in remission diagnoses are ok). Long term alcohol abusers are excluded as well (e.g., abused substance for more than 10 years).
 
• Any history of Autism Spectrum Disorder or Intellectual Disability.
 

Title: Clinical Investigation Plan		Author: [name]		Company Restricted	
DocID: ICBE-2-28674	Version: 2.0	Date: 2019-02-18	Status: Approved	Page: 9 of 35	
IRBMANAGER PILOT – QI PROJECT					

	
 
• The examinee must not be currently taking medication that might impact test performance (e.g., anti-convulsants, antipsychotics, benzodiazepines, psychostimulants, opioids, tricyclic antidepressants, some norepinephrine reuptake inhibitors). Most antihypertensive medications and statins are acceptable.
 
• If previously diagnosed with any physical condition or illness that might depress test performance, illness must not interfere with normal cognitive functioning at work, school, ADLs, etc. Diabetes, hypothyroidism, and hypertension are acceptable if controlled.
 

	
 
• Exclude primarily nonverbal or uncommunicative. Must not have a diagnosis of aphasia.
 
• Examinees should not have received neuropsychological testing although previous MMSE testing is allowed if more than 6 months prior
 
• Examinee must not be seeking medical diagnostic procedures for cognitive difficulties from a medical professional.
 
• Non-valid health insurance in USA.
 

Investigation design	
The study has a randomized, counterbalanced design with two conditions to which participants will be assigned randomly with minimization for demographic variables.

Investigation procedures	
The study consists of two phases. All participants in phase 1 will be invited to participate in two assessments that will take place with a time interval of two weeks between the two time points to minimize retest effects. Participants (total <math>N = 400</math>) will be randomly assigned to one of the following groups:
 
 
- Group A (<math>n=100</math>) completes digital tests in phase 1 and paper-pencil tests in phase 2,
 
- Group B (<math>n=100</math>) completes paper-pencil tests in phase 1 and digital tests in phase 2,
 
- Group C (<math>n=50</math>) completes digital tests in both phases,
 
- Group D (<math>n=50</math>) completes paper-pencil tests in both phases,
 
- Group E (<math>n=100</math>) only completes digital tests in one phase (50% of group E will be enrolled in phase 1 and the other 50% of group E will be enrolled in phase 2).
 
 
If the timeline allows for it, up to 50 additional participants aged 50-54 will be included in group E to stretch the age range for the regression-based norms, making the group size up to <math>n=150</math> and the total sample size up to <math>N = 450</math>.
 
The data of group A and B are used to compare score distributions within-subjects.
 
The data from groups A-D (phase 1) are used to compare score distributions between-subjects (aim 1).

Title: Clinical Investigation Plan		Author: [name]		Company Restricted	
DocID: ICBE-2-28674	Version: 2.0	Date: 2019-02-18	Status: Approved	Page: 10 of 35	
IRBMANAGER PILOT – QI PROJECT					

	
The data of group C and D are used to assess and compare test-retest reliability (aim 1) and assess reliable change indices (aim 3).
 
The data of group A (phase 1), group C (phase 1) and group E are used to estimate regression based norms for the digital tests (aim 3), as well as to estimate factor loadings for the structural equation model (aim 4).
 
The data of group A (phase 1), group B (phase 1), group C (phase 1) and group D (phase 1) are used to compare construct validity (aim 1).
 
Participants will be randomized with minimization for demographic variables (gender, age, education level, ethnicity).
 
Assuming a dropout rate of 20% we will oversample our desired N by the same percentage, resulting in sampling of 480 participants.
 
The completed tests will be scores by two well-trained raters, with double scoring of 30% of participants to assess inter-rater agreement.
 
Scoring algorithms for the ROCFT and the Clock Drawing Test are applied post-data collection. The scores estimated by the algorithms will be compared with manual scoring by a sample of well-trained raters (<math>n = 6</math>; aim 2). The data collected during this study are only used for validation and not used in any way to train these scoring algorithms.
 
Each assessment will last approximately 1.5 hours.

At-Home Subject Procedures
	
 NOT APPLICABLE


Devices
 
Check each box as appropriate and add a brief description of the device(s)—e.g., fitness tracker, VR goggles, breast pump, electric toothbrush, ELAN, MRI scanner.
 
Devices will be described fully in Section 2.1 of the study protocol.
	
 None
 
 Mock-up (see ICBE FAQ definition):
 
 Survey/questionnaire (if copyrighted, ensure permission for use):
 
Usability questionnaire
 
 Interview/focus group with audio/video taping**:
 
 Interview/focus group without audio/video taping**:
 
**see decision flowchart regarding interviews vs QI vs consulting https://share-intra.philips.com/sites/STS20131115093003/ICBE-FAQ/Lists/Photos/interviews%20criteria%20flowchart%20feb2018.pptx
 
 FDA or CE-approved medical device within intended use:
 
 FDA or CE-approved medical device outside intended use:
 
 FDA or CE-approved non-medical device within intended use:
 
The digital tests will be provided to the
 

Title: Clinical Investigation Plan		Author: [name]		Company Restricted	
DocID: ICBE-2-28674	Version: 2.0	Date: 2019-02-18	Status: Approved	Page: 11 of 35	
IRBMANAGER PILOT – QI PROJECT					

	
participants on an Ipad Pro (Apple). It has a screen size of 12.9-inch with a screen resolution of 2732x2048. Participants will use the Apple pencil for the Ipad Pro to perform the tests (see Figure). Both the iPad Pro as well as the Apple Pencil are wiped clean after use by each participant.
 
To digitally administer the digital tests to the participants, the test leader will start the test via the software prototype on a regular laptop that will be provided by Philips (see Figure).
 
The Ipad pro, Apple pencil and the regular laptop will all be commercially available devices and used within their intended use.

	
 FDA or CE-approved non-medical device outside intended use:
 
 In vitro medical device:
 
 Medical device prototype***:
 
 Non-medical device prototype***:
 
 Software prototype***, non-medical:
 
A selection of the digital tests are administered to the participants via a software prototype designed by Philips (Production Equivalent Device).
 
 Software prototype***, medical:
 
A selection of the digital tests is administered to the participants via a medical software prototype (on an iPad) designed by Philips (IntelliSpace Cognition).
 
 Other:
 <hr/> 
***Before a study employing prototypes may start, a Declaration of Conformity (DoC) needs to be issued by the Director Regulatory Affairs. With this DoC, Philips declares that the device can safely be used in the study. It may be needed to work according to some formal standards to build up this evidence (e.g. with respect to bio-compatibility or sterility).
 
*** DoC needed (brief overview of the actions that will be taken to get the Declaration of Conformity. See Philips Research QMS procedure "Procedure Product Release (QR-PRO-36)". Give details of how the project will deal with the regulatory requirements. Consult the Q&R office when needed):

Milestones
	
ICBE review will be completed 17 December 2018
 
IRB review will be completed 15 Feb 2019
 
Data collection will start in 15 March 2019
 
Data collection for time point 1 will be completed 15 June 2019 (with four examiners)
 
Data collection for time point 2 will be completed 15 Sept 2019 (with four examiners)
 
Data analysis will be completed 15 October 2019
 
Report will be completed 15 October 2019

Claims
	
Will you obtain regulatory (FDA, CE) approval for a new product or service, a new indication, or a new marketing claim?
 
 Yes  No N/A 510K exempt

Title: Clinical Investigation Plan		Author: [name]		Company Restricted	
DocID: ICBE-2-28674	Version: 2.0	Date: 2019-02-18	Status: Approved	Page: 12 of 35	
IRBMANAGER PILOT – QI PROJECT					

	
If YES, in what countries will the claims be registered?
 
  Netherlands     USA     Germany     China   India     Belgium     UK     Kenya   Other:         
 
Have you developed a list of claims that you would like to assert for your product or service?  Yes     No

External Research Ethics Committee (REC) Approval
 
Note: if your document is not in English or Dutch, include an English translation
	
  Not Required (not a local/state/country requirement)   Required (apply for it AFTER ICBE approval)   Approval already obtained (upload for review by ICBE)   REC Review is waived (upload review waiver)   REC has waived requirement for informed consent (upload waiver)   Check this box if more than one REC is involved in this study and identify them:         

Submission to Competent Authorities
	
 Not applicable (510K exempt)
 
Check the applicable option concerning Competent Authority approval for medical device studies:
 
  No submission to Competent Authority needed, since no non-released medical device involved   Approval from Competent Authority is mandatory for this study with a non-released medical device         
 
Note: Released medical device means a device that is e.g. CE-marked (93/42/EEC) if study takes place in EU, or has 510k if study takes place in USA.
 
Our device will be marketed as a Class-II Medical Device in the US. The device is 510(k) exempt by the FDA.          Link: https://www.accessdata.fda.gov/scripts/cdrh/cfdocs/cfPCD/classification.cfm?id=3768

Database registration
	
  None   ClinicalTrials.gov   Other:         


Type of Legal Agreement for this study
	
  None required     MRA Exhibit   Contract     Purchase Order          We will work with a CRO (supplier) via a purchase order and additional CRO agreement       

Status of Legal Agreement
	
  NA     Not started     In Process     In Place          Name of Legal Rep: [name]       

IP Strategy
	
See CRO agreement

ICBE Training is required for all key study personnel
	
  YES, this training is completed as required by ICBE*   NO, this training is not completed as required by ICBE*:         

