**6 CLINICAL INVESTIGATION DESIGN**

**6.1 General**

The study has a randomized, counterbalanced design and consists of two phases (see figure 1). We sample participants according to the sampling plan outlined below, to ensure representativeness of the sample. We will oversample by 20% to account for dropout or incomplete data (the *n*'s below represent the desired cell counts, after dropout).

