**Criteria and procedures for subject withdrawal or discontinuation**

Subjects will be enrolled when the inclusion criteria and exclusion criteria are met and when the subject has signed the informed consent form.

Subjects can leave the study at any time for any reason if they wish to do so without any consequences.

If one of the following criteria is fulfilled, the participation of a subject to the study is terminated:

- Subject indicates that he wishes to leave the study
- Subject is not able to use the iPad Pro (test data will not be destroyed but flagged as invalid)
- Subject does not meet inclusion/exclusion criteria anymore
- The investigator can decide to withdraw a subject from the study for medical reasons.

These subjects need to be replaced according to the sampling plan if test data of a subject are destroyed or test data are not complete due to study termination.

The point of enrolment is the time at which, following recruitment, a subject signs and dates the informed consent form. The first subject is expected to be enrolled in March 15 2019. The Clinical Investigation is expected to take 6 months.

The duration of each assessment is 90 minutes.

In this clinical investigation, the company that will recruit the participants will account for an expected dropout rate of 20%.

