**Clinical procedures**

Participants included in group A-D will be invited for an assessment on two different time points (phases). Both assessments will take approximately 1.5 hours. After signing an informed consent, participants will receive either all digital or all paper-pencil cognitive tests in phase 1 and either all digital or all paper-pencil cognitive tests in phase 2, depending on group assignment. See figure 1 for

Title: Clinical Investigation Plan		Author: [name]		Company Restricted
DocID: ICBE-2-28674	Version: 2.0	Date: 2019-02-18	Status: Approved	Page: 24 of 35
IRBMANAGER PILOT – QI PROJECT				

an overview of the study design. Participants included in group E of the study (see figure 1) will only receive one assessment (all digital cognitive tests). 50% of group E will be enrolled in phase 1 and the other 50% of group E will be enrolled in phase 2.

This assessment will take approximately 1.5 hours. All participants will be asked to complete a MoCA screener. The study will be concluded when each cell of the design (group A-E) meets its required sample size with participants that meet the inclusion criteria and completed the tests specified for their group.

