**Sample size**

The study will include a total of  $N = 400$  (up to  $N=450$ ) healthy individuals, without accounting for drop-out (see Figure 1 for the design); The tests will be scored by two well-trained raters. Moreover, to compute the inter-rater agreement between scoring algorithms and manual scoring we need six additional well-trained raters.

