**Expected drop-out rates**

The expected drop-out rate is 20%. The company that will recruit the participants will oversample by 20% to account for the drop-out rate, resulting in 80 additional participants recruited in addition to the 400 needed for the full design.

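### Recruiting 480 (400 plus 20%) does not cover the planned 20% drop-out: 384 completers are expected, 16 short of 400, and 480 covers at most 16.7% loss

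*Combined protocol and SAP*

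**What the plan says.** The recruitment figure appears in two places. The Executive Summary (Investigation procedures) states: "Assuming a dropout rate of 20% we will oversample our desired N by the same percentage, resulting in sampling of 480 participants". Section 7, Expected drop-out rates, repeats the 20% rate and the 20% oversample, "resulting in 80 additional participants recruited in addition to the 400 needed for the full design". Section 6.1 gives the percentage without the total: "We will oversample by 20% to account for dropout or incomplete data".

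Three places show what the 400 stands for:

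- Section 6.1 says that the group sizes "represent the desired cell counts, after dropout".
- Section 7, Sample size, gives 400 (up to 450) "healthy individuals, without accounting for drop-out".
- Section 6.4, Clinical procedures, ends the study when each group "meets its required sample size with participants that meet the inclusion criteria and completed the tests specified for their group".

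Two further rules bear on the consequence. Section 6.3, on withdrawal, says of subjects whose data are destroyed or incomplete: "These subjects need to be replaced according to the sampling plan". Section 7, on termination on statistical grounds, ends the study if 400 participants with the specified demographic distribution cannot be achieved.

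**The concern.** A 20% drop-out rate means that one in five of the people who enter do not finish. To finish with 400, the plan must start with 400 divided by the completing fraction, 0.80. It adds 20% of the target instead, which is always too few: the loss is taken from the larger, inflated number, so 20% of 480 is 96, not 80.

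At stake is whether the recruitment number delivers the plan's own required sample at the plan's own loss rate. If it does not, recruitment beyond 480 is the expected course of events and is not budgeted. The milestones are fixed (time point 1 complete by 15 June 2019, time point 2 by 15 September 2019), and a late replacement in groups A to D needs two visits. Section 10 names an increase in participants and an extension of study time as reasons for an amendment request, and section 9 requires IRB approval of an amendment before it is carried out. If 480 is taken as the approved number, which the protocol does not say, the shortfall makes such an amendment likely.

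**Working it through.** **Inputs.** Required completers: 400, made up of A 100, B 100, C 50, D 50 and E 100 (section 6.1). Drop-out rate: 20% (Executive Summary; section 7). Stated recruits: 480.

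**Reproducing the plan's figure.** 400 × (1 + 0.20) = 480. It matches exactly, so the rule used is target × (1 + rate).

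**What 480 delivers at 20% loss**

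- Expected completers: 480 × (1 − 0.20) = 384.
- Shortfall: 400 − 384 = 16, or 4% of the target.
- Largest loss that still leaves 400: 1 − 400/480 = 80/480 = 16.7%.
- Chance of at least 400 completers, with independent losses: P(Binomial(480, 0.80) ≥ 400) = 0.036.

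**What 20% loss needs**

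- 400 / (1 − 0.20) = 500 recruits, which is 100 extra, or 25% oversampling.
- For the optional total of 450: 450/0.80 = 562.5, so 563. The plan's rule would give 450 × 1.20 = 540. No oversample is stated for this case, and 480 would cover only 1 − 450/480 = 6.25% loss.

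**By group.** This assumes that the extra 80 are spread in proportion and that loss is equal in all groups; the plan states neither.

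| Group | Required | Recruited (× 1.20) | Completers (× 0.80) | Needed (÷ 0.80) |
|---|---|---|---|---|
| A | 100 | 120 | 96 | 125 |
| B | 100 | 120 | 96 | 125 |
| C | 50 | 60 | 48 | 62.5, so 63 |
| D | 50 | 60 | 48 | 62.5, so 63 |
| E | 100 | 120 | 96 | 125 |

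Rounding each group up gives 501 in the last column.

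**Effect on power if no one were replaced**

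- *Correlations.* Smallest r detectable with 80% power, two-sided alpha .05, by Fisher's z: r = tanh((1.960 + 0.842)/√(n − 3)). Groups A and B together: n = 200 gives .197 and n = 192 gives .201. Group C or D: n = 50 gives .387 and n = 48 gives .395. The plan's own figure for C or D is .37; the .387 is this calculation's baseline, and only the change of .008 matters here.
- *Equivalence test.* Assume a within-person difference with SD 1, one-sided alpha .05 and a true difference of zero. By normal approximation, power = 2Φ(b√n − 1.645) − 1. With b = .3, n = 200 gives 99.1% and n = 192 gives 98.8%. With b = .21, they give 81.5% and 79.4%. The n = 200 values agree with the 99% at ±.3 and the 80% at about ±.21 stated in section 7.

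**The case against.** The strongest reply is that 480 is a planning number and not a cap. Withdrawn subjects with destroyed or incomplete data are replaced, and the study closes only when every group is filled with completers. If those rules are followed, the analysed sample is protected and the termination rule is not triggered automatically. This stands, and it limits the point to recruitment planning.

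Secondly, the power effect is small even with no replacement. This also stands. Loss between visits mainly affects the within-subject comparison (A and B) and retest reliability (C and D); analyses of phase 1 data keep the first-visit results.

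Thirdly, group E attends once. If loss fell only on A to D, 300/0.80 + 100 = 475 recruits would be enough, and 480 would cover it. That requires at least 375 of the 480 to be placed in A to D. The plan states no such spread, and a proportional one puts 360 there and yields 360 × 0.80 = 288 against 300. The plan also applies its 20% to the whole 400 and counts incomplete data, which can arise in one visit. So this reading is possible but not the one written.

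Fourthly, 500 is no guarantee either. Under the same binomial assumption it gives at least 400 completers about 53% of the time, so it also leans on replacement. That is correct: 500 puts the expected number right and does no more.

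Finally, the 20% might be read as a share of completers, which would make 480 exact. No section defines it so, and it is called a drop-out rate throughout.

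**Conclusion.** The concern holds. The stated 480 does not deliver the required 400 at the stated 20% drop-out: the expected yield is 384, which is 16 short, and the break-even loss is 16.7%. This rests on 400 being a completer target, which sections 6.1, 6.4 and 7 support, and on the 20% applying to everyone recruited, as the plan writes it. The 3.6% chance also assumes independent losses.

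The error is certain but its statistical harm is small. The replacement and fill-every-group rules make recruitment past 480 the likely result, rather than a smaller analysed sample. It should be corrected because the figure appears in both the Executive Summary and section 7, and the recruiting company is told to plan on it.

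**What to change.** Amend the totals in the Executive Summary (Investigation procedures) and in section 7, Expected drop-out rates, together with the percentage in section 6.1, in one of two ways:

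1. **Keep 480.** State that it covers a drop-out of up to 16.7%, and that any further loss is made up under the replacement rule of section 6.3 and the completion rule of section 6.4. This is a change of wording with no extra planned participants. Its drawback is that recruitment beyond 480 stays open-ended if loss reaches 20%.
2. **Restate the figure as 500**, that is 25% oversampling, or 563 for the optional total of 450 if the same 20% allowance is meant to apply there. This adds 20 planned recruits to the 480 (for 450, 23 more than the 540 that the plan's rule would give). The allocation ratio is unchanged apart from rounding in groups C and D.

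In either case, state whether the 20% applies to single-visit group E and how the extra recruits are spread over the groups. No analysis changes.
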